3.9.2 Guidelines for Processing IND Safety Reports

The DF/HCC Sponsor will review all IND Safety Reports and ensure that all IND Safety Reports are distributed to the Participating Institutions. Participating Institutions will review and submit to their IRB according to their institutional policies and procedures.

3.10 Data Management

The DF/HCC ODQ/CTRIO develops case report forms (CRF/eCRFs), for use with the protocol. These forms are designed to collect data for each study. The DF/HCC ODQ/CTRIO provides a web based training for eCRF users.

3.10.1 Data Forms Review

Data submissions are monitored for timeliness and completeness of submission. Participating Institutions are notified of their data submission delinquencies in accordance with the following:

Incomplete or Questionable Data

If study forms are received with missing or questionable data, the submitting institution will receive a written or electronic query from the DF/HCC ODQ/CTRIO Data Analyst, Coordinating Center or designee. Responses to all queries should be completed and submitted within 14 calendar days. Responses may be returned on the written query or on an amended paper case report form, or in the case of electronic queries, within the electronic data capture (eDC) system. In the case of a written query for data submitted on a paper case report form, the query must be attached to the specific data being re-submitted in response.

Missing Forms

If study forms are not submitted on schedule, the Participating Institution will receive a Missing Form Report from the Coordinating Center noting the missing forms. These reports are compiled by the DF/HCC ODQ/CTRIO and distributed on a monthly basis.

4. REQUISITIONING INVESTIGATIONAL DRUG

The ordering of investigational agent is specified in the protocol section 8.

Participating Institutions should order their own agent.

Each site must ensure that the pharmacy will be able to receive and store the agent according to state and federal requirements. The local IRB should be kept informed of who will supply the agent (i.e., NCI or a pharmaceutical company) so that any regulatory responsibilities can be met in a timely fashion.

5. MONITORING: QUALITY CONTROL

The quality control process for a clinical trial requires verification of protocol compliance and data accuracy. The Coordinating Center, with the aid of the DF/HCC internal monitor will provide quality control oversight for the protocol.

5.1 Ongoing Monitoring of Protocol Compliance

The Participating Institutions may be required to submit participant source documents to the Coordinating Center for monitoring. Participating Institution may also be subject to on-site monitoring conducted by the Coordinating Center.

The Coordinating Center will implement ongoing monitoring activities to ensure that Participating Institutions are complying with regulatory and protocol requirements, data quality, and participant safety. Monitoring will occur before the clinical phase of the protocol begins, continue during protocol performance and through study completion. Additional monitoring practices may include but are not limited to; source verification, review and analysis of the following: eligibility requirements of all participants, informed consent procedures, adverse events and all associated documentation, study drug administration/treatment, regulatory files, protocol departures, pharmacy records, response assessments, and data management.

Participating institutions will be required to participate in Coordinating Center initiated teleconferences. A schedule of these calls is forthcoming.

Remote Monitoring

Participating Institutions will be required to forward de-identified copies of participants' medical record and source documents to the Coordinating Center to aid in source data verification. Random study subjects will be chosen for intermittent remote monitoring.

5.2 Monitoring Reports

The DF/HCC Sponsor will review all monitoring reports for on-site and remote monitoring of Participating Institutions to ensure protocol compliance. The DF/HCC Sponsor may increase the monitoring activities at Participating Institutions that are unable to comply with the protocol, DF/HCC Sponsor requirements or federal and local regulations. Participating Institutions may also be subject to an audit as determined by the DF/HCC Sponsor.

5.3 Accrual Monitoring

Prior to extending a protocol to an external site, the DF/HCC Sponsor will establish accrual requirements for each participating institution. Accrual will be monitored for each participating institution by the DF/HCC Sponsor or designee. Sites that are not meeting their accrual expectations may be subject to termination.

The accrual expectation for Stanford University School of Medicine is approximately 15 participants per year.

6. AUDITING: QUALITY ASSURANCE

Auditing is a method of Quality Assurance. Its main focus is to measure whether standards and procedures were followed. Auditing is the systematic and independent examination of all trial related activities and documents. Audits determine if evaluated activities were appropriately conducted and

whether data was generated, recorded and analyzed, and accurately reported per the protocol, Standard Operating Procedures (SOPs), and the Code of Federal Regulations (CFR).

6.1 Audit Plan: DF/HCC Sponsored Trials

One on-site audit will be scheduled by the ODQ/CTRIO, assuming at least three participants have been treated on protocol at the site. Approximately 3-4 participants would be audited at the site over a 2 day period. If violations which impact participant safety or the integrity of the study are found, more participant records may be audited.

6.2 Audit Notification

It is the Participating Institution's responsibility to notify the Coordinating Center of all scheduled audit dates (internal or NCI) and re-audit dates (if applicable), which involve this protocol. All institutions will forward a copy of final audit and/or re-audit reports and corrective action plans (if applicable) to the Coordinating Center, within 12 weeks after the audit date.

6.3 Audit Reports

The DF/HCC Sponsor will review all final audit reports and corrective action plans if applicable. The Coordinating Center, must forward these reports to the DF/HCC ODQ/CTRIO per DF/HCC policy for review by the DF/HCC Audit Committee. Based upon the audit assessments the DF/HCC Audit Committee could accept or conditionally accept the audit rating and final report. Conditional approval could require the DF/HCC Sponsor to implement recommendations or require further follow-up. For unacceptable audits, the DF/HCC Audit Committee would forward the final audit report and corrective action plan to the DFCI IRB as applicable.

6.4 Participating Institution Performance

The DF/HCC Sponsor, DFCI IRB, is charged with considering the totality of an institution's performance in considering institutional participation in the protocol.

6.4.1 Corrective Actions

Participating Institutions that fail to meet the performance goals of accrual, submission of timely and accurate data, adherence to protocol requirements, and compliance with state and federal regulations, may be recommended for a six-month probation period. Such institutions must respond with a corrective action plan and must demonstrate during the probation period that deficiencies have been corrected, as evidenced by the improved performance measures. Participating Institutions that fail to demonstrate significant improvement will be considered by the DF/HCC Sponsor for revocation of participation. A DF/HCC Sponsor and/or the DFCI IRB may terminate a site's participation if it is determined that a site is not fulfilling its responsibilities as described above.

APPENDIX E – Patient GVHD Survey

Identification (Name): Date:

chronic GVHD Symptom Scale

By circling one (1) number per line, please indicate how much you have been bothered by the following problems in the past month:

the fo	the following problems in the past month:					
SKIN:		Not at all	Slightly	Moderately	Quite a bit	Extremely
1.	Abnormal skin color	0	1	2	3	4
2.	Rashes	0	1	2	3	4
3.	Thickened skin	0	1	2	3	4
4.	Sores on skin	0	1	2	3	4
5.	Itchy skin	0	1	2	3	4
EYES	AND MOUTH:	Not at all	Slightly	Moderately	Quite a bit	Extremely
6.	Dry eyes	0	1	2	3	4
7.	Need to use eye drops frequently	0	1	2	3	4
8.	Difficulty seeing clearly	0	1	2	3	4
9.	Need to avoid certain foods due to mouth pain	0	1	2	3	4
10.	Ulcers in mouth	0	1	2	3	4
11.	Receiving nutrition from an intravenous line or feeding tube	0	1	2	3	4
BREA	ATHING:	Not at all	Slightly	Moderately	Quite a bit	Extremely
12.	Frequent cough	0	1	2	3	4
13.	Colored sputum	0	1	2	3	4
14.	Shortness of breath with exercise	0	1	2	3	4
15.	Shortness of breath at rest	0	1	2	3	4
16.	Need to use oxygen	0	1	2	3	4

EATING AND DIGESTION:		Not at all	Slightly	Moderately	Quite a bit	Extremely
17.	Difficulty swallowing solid foods	0	1	2	3	4
18.	Difficulty swallowing liquids	0	1	2	3	4
19.	Vomiting	0	1	2	3	4
20.	Weight loss	0	1	2	3	4
MUSC	LES AND JOINTS:	Not at all	Slightly	Moderately	Quite a bit	Extremely
21.	Joint and muscle aches	0	1	2	3	4
22.	Limited joint movement	0	1	2	3	4
23.	Muscle cramps	0	1	2	3	4
24.	Weak muscles	0	1	2	3	4
ENER	GY:	Not at all	Slightly	Moderately	Quite a bit	Extremely
25.	Loss of energy	0	1	2	3	4
26.	Need to sleep more/take naps	0	1	2	3	4
27.	Fevers	0	1	2	3	4
MENT	AL AND EMOTIONAL:	Not at all	Slightly	Moderately	Quite a bit	Extremely
28.	Depression	0	1	2	3	4
29.	Anxiety	0	1	2	3	4
30.	Difficulty sleeping	0	1	2	3	4

APPENDIX F – Provider GVHD Survey

Provider Assessment

Patient:	
MRN:	
Provider Name:	
Date of Visit:	
Study Timepoint:	

At this study timepoint, the patient has:

Documented aGVHD

(Proceed to assessment)

Documented cGVHD

(Proceed to assessment)

No Documented aGVHD or cGVHD

(Do not complete assessment)

	SCORE 0	SCORE 1	SCORE 2	SCORE 3
PERFORMANCE SCORE: KPS ECOG LPS	Asymptomatic and fully active (ECOG 0; KPS or LPS 100%)	Symptomatic, fully ambulatory, restricted only in physically strenuous activity (ECOG 1, KPS or LPS 80-90%)	Symptomatic, ambulatory, capab of self-care, >50% of waking hours o of bed (ECOG 2, KPS or LPS 60- 70%)	>50% of waking
SKIN† SCORE % BSA GVHD features to be score by BSA: Check all that apply: Maculopapular rash/erytl Lichen planus-like feature Sclerotic features Papulosquamous lesions ichthyosis Keratosis pilaris-like GV	involved hema res or	1-18% BSA	19-50% BSA	>50% BSA
SKIN FEATURES SCORE:	No sclerotic features		Superficial sclerotic features "not hidebound" (able to pinch)	Check all that apply: Deep sclerotic features "Hidebound" (unable to pinch) Impaired mobility Ulceration
Other skin GVHD features Check all that apply: Hyperpigmentation Hypopigmentation Poikiloderma Severe or generalized pr Hair involvement Nail involvement Abnormality present but	uritus	on-GVHD documented	cause (specify):	
MOUTH Lichen planus-like features present: Yes No Abnormality present but	No symptoms explained entirely by no	Mild symptoms with disease signs but not limiting oral intake significantly on-GVHD documented	disease signs with partial limitation of oral intake	Severe symptoms with disease signs on examination with major limitation of oral intake

	SCORE 0	SCORE 1	SCORE 2	SCORE 3
EYES Keratoconjunctivitis sicca (KCS) confirmed by ophthalmologist: Yes No Not examined	No symptoms	Mild dry eye symptoms not affecting ADL (requirement of lubricant eye drops ≤ 3 x per day)	Moderate dry eye symptoms partially affecting ADL (requiring lubricant eye drops > 3 x per day or punctal plugs), WITHOUT new vision impairment due to KCS	Severe dry eye symptoms significantly affecting ADL (special eyeware to relieve pain) OR unable to work because of ocular symptoms OR loss of vision due to KCS
Abnormality present bu	t explained entirely b	y non-GVHD documented	l cause (specify):	
GI Tract Check all that apply: Esophageal web/ proximal stricture or ring Dysphagia Anorexia Nausea Vomiting Diarrhea Weight loss ≥5%* Failure to thrive Abnormality present bu	No symptoms	Symptoms without significant weight loss* (<5%)	Symptoms associated with mild to moderate weight loss* (5-15%) OR moderate diarrhea without significant interference with daily living	Symptoms associated with significant weight loss* >15%, requires nutritional supplement for most calorie needs OR esophageal dilation OR severe diarrhea with significant interference with daily living
LIVER	Normal total bilirubin and ALT or AP < 3 x ULN	Normal total bilirubin with ALT ≥3 to 5 x ULN or AP ≥ 3 x ULN	Elevated total bilirubin but ≤3 mg/dL or ALT > 5 ULN	Elevated total bilirubin > 3 mg/dL
Abnormality present bu	t explained entirely b	y non-GVHD documented	l cause (specify):	
LUNGS** Symptom score :	No symptoms	Mild symptoms (shortness of breath after climbing one flight of steps)	Moderate symptoms (shortness of breath after walking on flat ground)	Severe symptoms (shortness of breath at rest; requiring 0_2)
Lung score: % FEV1	FEV1≥80%	FEV1 60-79%	FEV1 40-59%	FEV1 ≤39%
Pulmonary function tests Not performed Abnormality present bu	t explained entirely b	y non-GVHD documented	l cause (specify):	

S	CORE 0	SCORE 1	SCORE 2	SCORE 3	
P-ROM score (see below) Shoulder (1-7): Elbow (1-7): Wrist/finger (1-7): Ankle (1-4): Abnormality present but	No symptoms	Mild tightness of arms or legs, normal or mild decreased range of motion (ROM) AND not affecting ADL by by non-GVHD documents	Tightness of arms or legs OR joint contractures, erythema thought due to fasciitis, moderate decrease ROM AND mild to moderate limitation of ADL ented cause (specify):	Contractures WITH significant decrease of ROM AND significant limitation of ADL (unable to tie shoes, button shirts, dress self etc.)	
Not examined Currently sexually active Yes No	(See Supplemental figure [‡]) females with or without discomfort on exam may have or without symptoms with symptoms with discomfort on exam Not examined Verently sexually active Yes on exam discomfort on exam				
Abnormality present but				46-4	
Other indicators, clinical score to severity (0-3) bas					
Ascites (serositis)	Myast	henia Gravis			
Pericardial Effusion	Periph	eral Neuropathy	Eosino	philia > 500/μl	
Pleural Effusion(s)	Polym	yositis	Platele	ets <100,000/µl	
Nephrotic syndrome_	Weigh	nt loss>5%* without GI	symptoms Others	(specify):	
Overall GVHD Severity (Opinion of the evaluator)	□ No GV	THD Mild	☐ Moderate	☐ Severe	
Photographic Range of M	, ,				
1 (Worst) 2 3 4 5 6 7 (Normal) Shoulder 1 (Worst) 2 3 4 5 6 7 (Normal)					
	Elbow	EFF			
	Wrist/finger 1.00cm	3 4 5	6 7 (Normal)		
	Ankle	2 3 4(Normal)			

- † Skin scoring should use both percentage of BSA involved by disease signs and the cutaneous features scales. When a discrepancy exists between the percentage of total body surface (BSA) score and the skin feature score, OR if superficial sclerotic features are present (Score 2), but there is impaired mobility or ulceration (Score 3), the higher level should be used for the final skin scoring.
- * Weight loss within 3 months.
- **Lung scoring should be performed using both the symptoms and FEV1 scores whenever possible. FEV1 should be used in the final lung scoring where there is discrepancy between symptoms and FEV1 scores.
 Abbreviations: ECOG (Eastern Cooperative Oncology Group), KPS (Karnofsky Performance Status), LPS (Lansky Performance Status); BSA (body surface area); ADL (activities of daily living); LFTs (liver function tests); AP

(alkaline phosphatase); ALT (alanine aminotransferase); ULN (normal upper limit). ‡ To be completed by specialist or trained medical providers (see Supplemental Figure).

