5.9 Criteria for Taking a Participant Off Protocol Therapy

The following are criteria for removing a participant from active study:

- The development of steroid-requiring cGVHD
- Malignant disease progression
- Intercurrent illness that prevents further administration of treatment
- Unacceptable adverse event(s)
- Participant demonstrates an inability or unwillingness to comply with the treatment regimen
- Participant decides to withdraw from the protocol therapy
- General or specific changes in the participant's condition render the participant unacceptable for further treatment in the judgment of the treating investigator

Participants will be removed from the protocol therapy when any of these criteria apply. The reason for removal from protocol therapy, and the date the participant was removed, must be documented in the case report form (CRF). Patients with steroid-requiring cGVHD, unacceptable AEs or intercurrent illness preventing further drug administration who come off treatment should continue to have laboratory studies and clinical assessments performed at the appropriate timepoints. Patients with malignant disease progression do not require laboratory or clinical follow-up. Alternative care options will be discussed with the participant.

An ODQ/CTRIO Treatment Ended/Off Study Form will be filled out when a participant is removed from protocol therapy. This form can be found on the ODQ/CTRIO website or obtained from the ODQ/CTRIO registration staff.

In the event of unusual or life-threatening complications, treating investigators must immediately notify the Overall PI, [name] at [contact] [name].

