12.7 Analysis of Secondary Endpoints

Secondary objectives include to determine the overall cGVHD rate after HCT, NIH moderate-severe cGVHD rate after HCT, cumulative incidence of non-relapse mortality and relapse, adverse hematologic events and infections, immunosuppression-free survival (IFS) at 1 and 2 years from transplantation, progression-free and overall survival at 1 and 2 years from transplantation, and immunologic correlates of B cell depletion.

For the comparison of GVHD, NRM and relapse, competing risks data analysis will be performed using Gray test²⁶ and Fine and Gray competing risks regression analysis²⁵. For PFS, OS, and IFS, standard survival analysis will be performed. Adverse hematologic events will be compared by cumulative incidence measures. All analysis will be repeated by disease group (myeloid vs. lymphoid).

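### The NIH moderate-severe cGVHD endpoint needs the first time that grade is reached, but the only severity form records current status at five visits, so some episodes can be missed or dated late

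*Combined protocol and SAP*

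**What the plan says.** Section 12.7 lists the "NIH moderate-severe cGVHD rate after HCT" among the secondary objectives and gives its analysis in one line: "For the comparison of GVHD, NRM and relapse, competing risks data analysis will be performed using Gray test", together with Fine and Gray regression. It does not define the event or say how it is dated.

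The Study Calendar (Section 10, with footnote 9) places the chronic GVHD assessment and the provider survey at months 6, 9, 12, 18 and 24. The survey itself, Appendix F, opens with "At this study timepoint, the patient has" and three options. Documented acute or chronic GVHD leads on to organ scoring. The third option, "No Documented aGVHD or cGVHD", carries the instruction "Do not complete assessment". Neither the organ scores nor the single overall severity box, which is the evaluator's opinion, has a worst-since-last-visit or onset-date field. The only look-back item on the form is weight loss over 3 months.

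Under Section 5.9, patients who stop treatment for steroid-requiring cGVHD "should continue to have laboratory studies and clinical assessments performed at the appropriate timepoints". That keeps them in assessment, but on the fixed schedule. Nothing calls for scoring at onset or when systemic steroids start.

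**The concern.** A cumulative incidence counts a patient at the first time the state is reached, whatever happens later. A current-status form shows only what is present on the visit day. Section 2.1 names systemic corticosteroids as the mainstay of cGVHD treatment, and they can start between visits. A patient may therefore reach moderate grade, improve on treatment, and be scored as mild or not scored at the next visit. The endpoint would then mix incidence with response to treatment. This is the severity endpoint that gives context to a primary endpoint based on steroid use, so its meaning should be clear before data are collected. A peak grade not recorded at the time may be hard to reconstruct later.

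**Working it through.** **1. What the analysis needs against what is collected**

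| Needed for Section 12.7 | Source in the documents |
|---|---|
| Was moderate or severe grade ever reached? | Appendix F: grade on the visit day only |
| Date it was first reached | No field in Appendix F. Section 5.9 requires the off-therapy date, which carries no grade |
| Derivation rule | None stated |

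**2. Gaps between scorings.** Counting from the first dose at month 3: 6−3, 9−6 and 12−9 give 3 months each; 18−12 and 24−18 give 6 months each.

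**3. Three paths for a patient who reaches moderate grade at month 7** (hypothetical):
- Still moderate at month 9: counted, but dated up to 2 months late if the visit date is used.
- Mild at month 9, moderate again at month 12, 18 or 24: counted, dated later still.
- Below moderate at month 9 and at every later scoring: not counted. If GVHD has resolved, the third option on the form may apply and no scores are entered at all.

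**4. How often an episode would contain a scoring.** Assume onset uniform over months 3 to 24, visits exactly on schedule, 30.4375 days per month, and one episode lasting d months (d below 3). The share with no scoring while at that grade is 1 − 5d/21. For onsets in months 3 to 12 it is 1 − 3d/9.

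| Duration | d (months) | Months 3–24 | Months 3–12 |
|---|---|---|---|
| 4 weeks | 0.92 | 78% | 69% |
| 8 weeks | 1.84 | 56% | 39% |
| 13 weeks | 2.99 | 29% | about 0% |

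The durations are assumptions; the documents give none. These shares also exceed the share of patients lost, because a patient can return to moderate grade at a later visit.

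**5. Effect on the comparison.** The plan's only power figure concerns the primary endpoint (Section 12.2: 38% vs 21%, 200 patients, two-sided 0.1, Fisher's exact test, 80%). Exact enumeration with 100 per arm gives 80.8%, so it reproduces. The documents state no rate or power for the NIH endpoint, so 38% and 21% serve here only as stand-ins. With a loss L equal in both arms, each rate is multiplied by (1 − L):

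| L | Recorded rates | Difference (points) | Ratio |
|---|---|---|---|
| 0 | 38.0% vs 21.0% | 17.0 | 0.55 |
| 10% | 34.2% vs 18.9% | 15.3 | 0.55 |
| 20% | 30.4% vs 16.8% | 13.6 | 0.55 |
| 30% | 26.6% vs 14.7% | 11.9 | 0.55 |
| 40% | 22.8% vs 12.6% | 10.2 | 0.55 |

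Under proportional subdistribution hazards, ln(1 − 0.21)/ln(1 − 0.38) = 0.49 with no loss, and ln(1 − 0.126)/ln(1 − 0.228) = 0.52 at 40% loss. The planned relative estimate hardly moves under equal loss.

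**The case against.** The case on the other side has real force.

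- **Case report forms.** Appendix D, Section 3.10 says separate forms are developed for the protocol. They are not in the documents and may hold an onset date or a maximum grade. This stands. The point is that the protocol requires neither, and that Appendix F is the only severity instrument it shows.
- **Dates.** A reader might infer that onset is rounded to visit dates. The documents do not say so. Section 5.9 requires the date and reason for leaving protocol therapy, which dates steroid-requiring cases during the dosing period. It gives no grade, and after the month-12 dose there is no treatment left to stop, which is where the 6-month gaps begin.
- **The screening question on the form.** A reader might infer that only previously diagnosed GVHD is scored. A case first recognised at the visit goes on to scoring, and so does documented acute GVHD. The question matters mainly for GVHD that has resolved since the last visit.
- **Persistence.** Section 2.1 describes steroid responses as incomplete, and in the cited pilot of rituximab plus prednisone the response rate was 40% at 6 and 12 months. Many moderate cases may still be moderate at the next visit, which argues against the upper end of the loss range.
- **Magnitude.** The stand-in rates belong to another endpoint, the loss shares have no source, and Fisher's test is not planned here. A claim that this endpoint, or the trial, loses a given amount of power is not supported.

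None of this supplies a rule for deriving the event or its date.

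**Conclusion.** The point holds in a limited form. Followed as written, Appendix F can miss episodes that reach moderate or severe grade between visits and are below it at all later scorings, and it can date others late. It does not miss every case treated between visits. The size is unknown: the 15.3 to 10.2 point range assumes 38% vs 21% as true rates and an equal proportional loss of 10% to 40%, none of which the documents give for this endpoint. Under equal loss the absolute difference shrinks while the ratio stays at 0.55. If the losses differed between arms the ratio would move as well, but the documents give no basis for a figure. The primary endpoint and its stated 80% power are unaffected. This is a cheap improvement to a secondary endpoint.

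**What to change.** Add to Appendix F, at each scheduled visit, the worst NIH organ scores and overall grade since the last visit, and the date that grade was first reached. Have these fields completed also for patients whose GVHD has resolved since the last visit. In Section 12.7, define the endpoint as first attainment of NIH moderate or severe grade, taken from those fields. There is no need to score patients who have never had GVHD.

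Optionally, complete the form also at cGVHD diagnosis or when systemic steroids start. Use data already available: lung function is scheduled only at screening and months 12 and 24, and no extra test should be required.

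The cost is a few fields at existing visits and some recall error. The optional form would add roughly 59 forms if tied to steroid-requiring cGVHD by one year (38 + 21 per 100 at the Section 12.2 rates). It would add about 108 if tied to any cGVHD by two years (48 + 60 per 100 at the rates cited in Section 2.1 for the earlier rituximab study).
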